5.3.4 Drug Supply Records

Accurate accounting of all study medication must be maintained. Drug disposition records must be kept in compliance with applicable guidelines and regulations.

6 Treatment Plan**6.1 Overview****6.1.1 Acalabrutinib Plus Obinutuzumab**

In the Phase 1b dose-escalation portion of the study, 2 cohorts (Cohort 1, relapsed/refractory and Cohort 2, treatment-naive) will be evaluated with slightly staggered enrollment. First, 6 subjects with relapsed/refractory CLL will be enrolled into Cohort 1. Once the safety has been evaluated, the relapsed/refractory cohort will be expanded to 26 subjects and enrollment of 6 treatment-naive subjects can begin in Cohort 2. Once safety is established for Cohort 2, then the cohort will be expanded to 19 subjects (Phase 1b expansion portion).

Each cycle will be [REDACTED]

Acalabrutinib will be administered starting [REDACTED] and will be administered [REDACTED] until disease progression.

Obinutuzumab will be given in the standard dosing fashion starting on [REDACTED] cci [REDACTED] On [REDACTED] cci [REDACTED] subjects will receive [REDACTED] cci [REDACTED] IV. On [REDACTED] cci [REDACTED] subjects will receive [REDACTED] cci [REDACTED] On [REDACTED] cci [REDACTED] subjects will receive [REDACTED] cci [REDACTED] IV. On [REDACTED] cci [REDACTED] subjects will receive [REDACTED] cci [REDACTED] of each cycle. For subjects treated at [REDACTED] cci [REDACTED] will be given on [REDACTED] cci [REDACTED] and [REDACTED] cci [REDACTED] on [REDACTED] cci [REDACTED] On [REDACTED] cci [REDACTED] subjects will receive [REDACTED] cci [REDACTED] IV and during [REDACTED] cci [REDACTED] subjects will receive [REDACTED] cci [REDACTED] on [REDACTED] cci [REDACTED] of each cycle.

It is acceptable for cycles to begin [REDACTED] cci [REDACTED] of a new cycle. For example, if the treatment due date is a [REDACTED] cci [REDACTED]

[REDACTED] New cycles can be started up to [REDACTED] cci [REDACTED] the protocol-defined date for major life events (e.g., serious illness in a family member, major holiday, vacation that cannot be rescheduled). Documentation to justify a delay or advance of a cycle should be provided.

In Cohorts 1 and 2, subjects who achieve a bone marrow MRD-negative CR have the option to discontinue acalabrutinib.

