Peripheral blood flow cytometry will be performed serially to analyze how B, T, and NK cell total number and subset composition change during the course of this therapy. As well, T cells and NK cells will be selected from peripheral blood at baseline and serial time points to determine how cytokine expression, cytotoxicity directed by NK cells (direct or antibody mediated), NK cell direct cytotoxicity, activation markers of T-cells and NK cells, or T cell polarity is changed by acalabrutinib alone or in combination with obinutuzumab, rituximab, or venetoclax.

The expression of cell death pathway proteins such as MCL1, BCL-2 and others will be measured from peripheral blood using flow cytometry on serial sample to determine if the level of cell death proteins change with treatment and if a profile of cell death proteins is predictive of treatment outcomes.

CCI

[REDACTED]

[REDACTED]

MRD status will be evaluated in all subjects at prespecified time points. In Cohorts 1 and 2, all subjects should have bone marrow biopsy with MRD analysis at Cycle 12 Day 1 ([Table 11](#)). **CCI**

[REDACTED]

[REDACTED]

Figure 2: 

CCI

[figure not shown]

Figure 3: 

CCI

All samples, except PK samples outlined in [Section 13.3](#), will be delivered to the CLL Experimental Therapeutics Laboratory for processing and shipment of selected samples.

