14.1 Study Overview

This is a Phase 1b study with expansion to evaluate the safety and preliminary efficacy of acalabrutinib in combination with obinutuzumab, or with venetoclax and an anti-CD20 antibody (rituximab or obinutuzumab) in 4 separate cohorts of subjects: those with relapsed/refractory CLL (Cohorts 1 and 3) and those with treatment-naive CLL (Cohorts 2 and 4). Enrollment will begin in Cohort 1, where the recommended dose will be based on decision rules from a standard 3+3 Phase 1 trial design and will proceed as outlined in [Figure 4](#). Both Cohorts 1 and 2 will be expanded to better evaluate the toxicity profile of these combination regimens, and also to detect moderate to large increases in ORR at 12 months relative to historical control. Cohorts 3 and 4 will be enrolled to establish the safety profile of the combination of acalabrutinib plus venetoclax plus an anti-CD20 antibody. The ORR will be defined as the proportion of treated subjects who achieve complete or partial remission at Cycle 16 for Cohorts 3 and 4. The cumulative ORR over time will be summarized for each of the 4 cohorts individually.

Figure 4: Trial Design

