14.6 Analysis Plan

14.6.1 Primary Endpoints

For Cohorts 1 and 2, the ORR (PR or better) at the 12-month response assessment will be calculated and 95% exact binomial CIs will be provided. For Cohorts 1 to 4, toxicities will be tabulated by type and grade using NCI-CTCAE version 4.03 criteria or higher and displayed in summary form. In addition, the number of subjects requiring dose reductions, and the reason for going off each treatment may be summarized.

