7.3 Analysis Windows

For parameters summarized by visit, an analysis window will be assigned to each nominal visit. Each assessment will be assigned to an analysis visit based on the analysis window in which the assessment date falls. Details are defined in [Appendix A](#).

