7.4 Missing Data Handling

No imputation for missing values of efficacy endpoints. Imputation for missing dates such as AE start or end dates and prior and concomitant medication start dates or end dates will be documented in the programming specifications.

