12.1 Primary Efficacy Endpoint and Analysis

12.1.1 Overall Response Rate (ORR)

ORR is the proportion of subjects who achieve complete remission (CR), CR with incomplete bone marrow recovery (CRI), nodular partial remission(nPR), or partial remission (PR) while on treatment before the initiation of new anticancer therapy or stem cell transplant.

For Cohorts 1 and 2, the ORR(PR or better) at the all available response assessments up to the 12-months will be calculated and 95% exact binomial CIs will be provided.

ORR will be summarized using All Treated Population and Efficacy Evaluable Population.

For CLL disease subgroups, ORR, including PRL as a response, (only for Cohorts 1 and 2), will also be summarized in the same fashion.

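### SAP 12.1.1 turns the Cohort 1 and 2 primary ORR into what reads as a cumulative rate up to 12 months, where Protocol 14.6.1 takes it at the 12-month assessment

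*SAP*

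**What the plan says.** Protocol 14.6.1 gives the primary efficacy analysis: "For Cohorts 1 and 2, the ORR (PR or better) at the 12-month response assessment will be calculated". Protocol 14.4 and SAP 4.0 both place the 50% null at the 12-month evaluation, in the same text as the 16/26 and 12/19 cut-offs. Protocol 14.1 names a different quantity as a separate summary: "The cumulative ORR over time will be summarized for each of the 4 cohorts individually".

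SAP 12.1.1 first defines ORR as the proportion who achieve CR, CRi, nPR or PR "while on treatment before the initiation of new anticancer therapy or stem cell transplant". For Cohorts 1 and 2 it then says that "the ORR(PR or better) at the all available response assessments up to the 12-months will be calculated". The SAP gives no reason for the different timing. Its introduction attributes the update to the Amendment 7 changes on stopping and restarting acalabrutinib. For Cohorts 3 and 4, SAP 12.2.1 does name a single time point, Cycle 16.

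Other text bears on how a 12-month rate would be computed:

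- SAP 7.3: "Each assessment will be assigned to an analysis visit based on the analysis window in which the assessment date falls". Appendix A lists the windows.
- SAP 7.4: "No imputation for missing values of efficacy endpoints".
- Protocol 6.1.1, repeated in 6.7: "In Cohorts 1 and 2, subjects who achieve a bone marrow MRD-negative CR have the option to discontinue acalabrutinib".
- Protocol Table 11, footnote B, moves the fourth 12-weekly evaluation to Cycle 12 Day 1. Protocol 13.1 adds: "In Cohorts 1 and 2, all subjects should have bone marrow biopsy with MRD analysis at Cycle 12 Day 1".

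**The concern.** A rate at 12 months and a rate up to 12 months answer different questions. The first counts subjects in response at a fixed time. The second counts subjects who were in response at any time by then, including those who later lost the response or were not assessed at the landmark. The protocol keeps the two apart. The SAP sentence, on its natural reading, makes the second one primary.

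If the SAP is followed as written, the headline ORR and its exact interval for Cohorts 1 and 2 describe a quantity the protocol did not name as primary. SAP 4.0 still carries cut-offs framed at the 12-month evaluation, so a reader may compare the cumulative count with a rule written for something else. The primary objectives in both documents say only that ORR is determined at 12 months, and that wording fits either version.

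**Working it through.** **1. The plan's own design figures.** Inputs are from Protocol 14.4 and SAP 4.0: null 50%, alternatives 75% (relapsed/refractory) and 80% (treatment-naive), promising if more than 16 of 26 or more than 12 of 19 respond. Exact binomial tails:

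- Cohort 1: P(X ≥ 17 | n = 26, p = 0.50) = 0.084; P(X ≥ 17 | p = 0.75) = 0.909.
- Cohort 2: P(X ≥ 13 | n = 19, p = 0.50) = 0.084; P(X ≥ 13 | p = 0.80) = 0.932.

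These reproduce the stated one-sided 0.10 and 90% power, with each alternative matched to its population. They belong to a count whose null is set at the 12-month evaluation.

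**2. Which visit is the 12-month visit.** With 28-day cycles, Day 1 of cycle k is study day (k − 1) × 28 + 1, which agrees with Appendix A for Cohorts 1 and 2:

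| Visit | Study day | Appendix A window | Days before C12D1 |
|---|---|---|---|
| C4D1 | 85 | to 127 | 224 |
| C7D1 | 169 | 128–211 | 140 |
| C10D1 | 253 | 212–281 | 56 |
| C12D1 | 309 | 282–351 | – |
| C15D1 | 393 | 352–435 | – |

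Footnote B and the Cycle 12 marrow point to C12D1. Day 365 falls in the C15D1 window. No text says which window is the 12-month assessment.

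**3. Direction.** Let L be the number in response at the landmark, and E the number with an earlier response that is lost or unassessed there. If the landmark lies within the first 12 months, the subjects, response category and on-treatment rule are the same, and unassessed subjects count as non-responders, then the cumulative count is L + E with E ≥ 0. It cannot be lower than L. If the landmark were a C15D1 assessment after Day 365, or the landmark rate used only assessed subjects, the direction is not certain.

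**4. Size per subject.** 1/26 = 3.8 points in Cohort 1; 1/19 = 5.3 points in Cohort 2. One such subject at the cut-off, with exact (Clopper-Pearson) 95% intervals:

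| Cohort | Landmark count | Count with E = 1 |
|---|---|---|
| 1 | 16/26 = 61.5% (40.6–79.8) | 17/26 = 65.4% (44.3–82.8) |
| 2 | 12/19 = 63.2% (38.4–83.7) | 13/19 = 68.4% (43.4–87.4) |

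**5. Can E exceed zero?** Protocol Section 9 requires CR and PR to persist for at least 2 months. That limits losses but does not exclude them, because C4D1 and C7D1 precede C12D1 by 224 and 140 days. A missed C12D1 assessment also adds to E. The documents give no value for E.

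**6. The by-visit reading.** Read with SAP 7.3, the sentence could mean a rate at each scheduled visit. It would then give four rates (C4, C7, C10 and C12 Day 1), and SAP 12.1.1 does not say which is primary.

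**7. What a landmark rate needs that is not written.**

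- The window (step 2).
- The denominator: SAP 7.4 rules out imputation but does not say whether a subject unassessed in the window stays in.
- The on-treatment clause: it does not say how a subject who stopped acalabrutinib in marrow MRD-negative CR is counted at the landmark.

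**The case against.** The strongest defence is that the SAP sentence is badly worded, not a changed endpoint. The verb in the SAP definition does not settle the matter, because Protocol 14.1 also speaks of subjects who achieve remission when it defines a point-in-time rate at Cycle 16. On a by-visit reading the last of the four rates would be the protocol's rate, and the SAP's own objectives and Section 4.0 would point to it. The effect may be nil: no test is planned (SAP 7.1), the number of affected subjects is unknown, and the 2-month rule leaves little room for loss after C10D1. The null counts PRL as response and the primary endpoint does not, so any upward shift against the cut-offs can be fully offset. The three open items arise mainly once a landmark is adopted. The schedule favours C12D1, subjects without a documented response can be taken as non-responders in a defined population, and few would stop in MRD-negative CR before the scheduled Cycle 12 marrow.

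Much of this stands. The wording is garbled, the size is unknown, C12D1 is the likelier window, and the non-responder rule is a recommendation that the documents do not prescribe. It does not clear the text. On either reading SAP 12.1.1 fails to designate the 12-month rate as primary, and nothing records or explains the difference. The three items may be small on their own, but a landmark analysis cannot be programmed unambiguously without them.

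**Conclusion.** The concern holds and should be fixed. Followed as written, SAP 12.1.1 reports as primary a quantity other than the one in Protocol 14.6.1, or, on the by-visit reading, leaves the primary rate undesignated.

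Under the conditions in step 3, any difference is upward, by 3.8 points per affected subject in Cohort 1 and 5.3 points in Cohort 2. The number of affected subjects is not known and may be zero. The consequence is for the reported estimate, its interval and any informal comparison with the cut-offs. No change in the probability of passing the cut-offs is claimed. That would need an assumed share of lost or unassessed early responders, and the PRL difference acts the other way.

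**What to change.** In SAP 12.1.1, define the Cohort 1 and 2 primary ORR as PR or better at one designated 12-month assessment, and:

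- name its Appendix A window (C12D1, Day 282–351, if footnote B of Protocol Table 11 intends that visit);
- in the All Treated Population, count subjects with earlier progression, earlier new anticancer therapy or no assessment in the window as non-responders;
- state how the on-treatment clause applies at the landmark to subjects who stopped acalabrutinib in MRD-negative CR;
- report best response up to 12 months as supportive.

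If the cumulative definition is what the sponsor wants, record it with a reason as a change from the protocol and do not read it against 16/26 and 12/19.

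The cost is SAP wording and a re-run of the ORR tables for Cohorts 1 and 2, covering two populations and the version that includes PRL. The reported ORR may come out slightly lower, and counting unassessed subjects as non-responders can lower it further.

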12.2 Secondary Efficacy Endpoints and Analyses

The secondary efficacy analyses will be performed using All Treated Population.

12.2.1 Overall Response Rate(ORR)

The ORR of the combination therapy of acalabrutinib plus venetoclax plus an anti-CD20 antibody at Cycle 16 (Cohorts 3 and 4) will be calculated and 95% exact binomial CIs will be provided

12.2.2 Complete Response Rate and MRD-Negative Complete Response Rate

The CR rate will be calculated and corresponding 95% confidence intervals through use of exact binomial distribution will be provided. The MRD-Negative CR rate will be summarized with MRD data in separate report..

12.2.3 Progression-Free Survival

PFS is defined as the time from the date of first dose to the date of first disease progression or death due to any cause, whichever comes first. If no disease progression or death is reported for a subject, the subject will be censored at the date of last adequate assessment (censoring date). If a subject receives an autologous or allogeneic stem cell transplant, the subject will be censored at the date of transplant. If a subject starts new anticancer therapy before disease progression or death, the subject will be censored at the date of last adequate assessment prior to receiving the new anticancer therapy. Adequate assessment is defined as physical examination (PE) and complete blood count (CBC) or computed tomography (CT) for CLL disease subgroups (or PET-CT for RS/PLL disease subgroup) and CBC. If a subject does not have any adequate assessment after first dose, the subject will be censored at Day 1.

PFS is calculated as date of disease progression or death (or censoring date for censored subjects) - first dose date + 1.

Events and censoring rules for PFS are summarized as follows:

Situation	Outcome	Date	Event Description/ Censoring Reason
Documented Progression of Disease (PD)	Event	Earliest date of disease assessment documenting PD	PD
Death	Event	Date of Death	Death
Start of new anticancer therapy before documented PD or death	Censored	Date of last adequate assessment prior to receiving the new anticancer therapy	New anticancer therapy

Start of transplant	Censored	Date of transplant	Transplant
Withdrawal of consent before documented PD or death	Censored	Date of last adequate disease assessment	Withdrawal of consent
Lost to follow-up before documented PD or death	Censored	Date of last adequate disease assessment	Lost to follow-up
No documented PD or death and the reason for not completing Safety Follow-up visit is “Other”	Censored	Date of last adequate disease assessment	Other: specify
No documented PD or death at the time of data cutoff	Censored	Date of last adequate disease assessment	Data cutoff
No post-baseline adequate disease assessments	Censored	Date of first dose	No post-baseline adequate disease assessments

Kaplan-Meier (KM) curve will be used to estimate the distribution of PFS. Median PFS and the 95% confidence limits and PFS rates for selected landmarks with 95% CIs will be reported. Number of progressions, deaths, and censored events by reason will be summarized.

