the reduction guidelines in [Table 9](#). Missed doses should not be made up. Subjects who are stable at a lower dose for [CCI](#) may be dose-escalated by 1 dose level.

For Grade ≥ 3 nonhematologic toxicity in Cycles 1 and 2 or despite following recommendations for venetoclax, please follow the guidelines noted in [Section 7.2.2](#) for acalabrutinib and/or obinutuzumab.

For \geq Grade 3 nonhematologic toxicity for which individual study drug attribution is not possible, subjects should have all drugs held until toxicity resolves to \leq Grade 1, and then subjects should be restarted at 1 dose level lower again using [Table 10](#). Subjects who are stable at a lower dose level for [CCI](#) may be dose-escalated by 1 dose level.

Table 9: Dose Modification for Toxicity During Venetoclax Treatment (Cohorts 3 and 4)

Dose at Interruption, mg	Restart Dose, mg ^a
CCI	

^a During the [CCI](#) continue the reduced dose for [CCI](#) before increasing the dose.

Table 10: Dose Adjustments for All Other Nonhematologic Toxicities for Which Individual Study Drug Attribution is Not Possible (All Cohorts)

Dose Level	Acalabrutinib Dose	Rituximab Dose	Obinutuzumab Dose	Venetoclax ^a
CCI				

^a During the [CCI](#) continue the reduced dose for [CCI](#) before increasing the dose.

8 Schedule of Activities

Table 11. Schedule of Activities: Cohorts 1 and 2

Tests & Observations (all labs listed here are standard of care except those labeled correlative studies and PK)	Screening	Day 1, 8, 15 of Cycle 1	Day 2 of Cycle 1	Day 1 of Cycles 2-12	Day 1 of Cycles 15, 18, 21, 24 ^H	Relapse/ Disease progression	Safety Follow-up ^I	Discontinua- tion Follow-up ^J	Long-term Follow-up ^K
ACP-196 CCI ¹ PO administration		CCI							
Obinutuzumab administration									
History & physical examination with tumor measurements ¹	X	X		X	X	X	X		
Height	X								
Weight	X	X		X	X	X	X		
ECOG PS	X	X		X	X	X	X		
2 buccal swabs	X								
ECG ²	X								
Concomitant medications	X	X	X	X	X	X	X	X	
Adverse events	X	X	X	X	X	X	X	X	
FISH/stimulated karyotype ³	X					X			
Zap-70 methylation ⁴	X								
IGHV mutational status ⁴	X								
Complete blood count (CBC)	X	X		X	X	X	X		
Chem 10	X	X		X	X		X		
Liver function panel	X	X		X	X		X		
LDH, uric acid	X	X		X	X		X		
Beta-2-microglobulin	X								
Direct antiglobulin test (Coomb's test)	X								

Table 11. Schedule of Activities: Cohorts 1 and 2

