 - B. Response evaluations will be done every 12 weeks from randomization for the first 24 months (with the 4th evaluation shifted to Cycle 12 Day 1 rather than Cycle 13 Day 1, to align with study visits), and then every 24 weeks thereafter. Hematology results must be done within 7 days of CT scans. Bone marrow biopsies/aspirates to confirm a CR must be done within 4 weeks of the CT scan, which showed CR.
 - C. PB samples will be used to evaluate for MRD every 3 cycles (at the discretion of the investigator, in line with scheduled response assessments, per protocol).
 - D. Specific times and tube types for correlative samples are outlined in [Section 13.2](#).
 - E. PK analysis will be performed on the first 8 expansion group patients of Cohort 1. Schedule can be found in [Section 13.3](#).
 - F. If performed as part of relapse analysis
 - G. As outlined in [Section 13.4](#)
 - H. Visits to continue every 6 cycles thereafter (\pm 7 days).
 - I. A safety follow-up (SFU) visit is required for all subjects 30 days (+7) from the last dose of study drug.
 - J. After discontinuation of study treatment for any reason, each subject should be followed until disease progression or the start of alternative anticancer therapy. If disease progression has not occurred at the time of the 30-day SFU visit, discontinuation follow-up (DFU) visits should occur approximately every 12 weeks until disease progression. During this period, subjects will be followed via CT scans every 24 weeks; after 2 years in DFU, CT scans will be yearly. AE and concomitant medication reporting, irrespective of seriousness, ends 30 days after the last dose of study drug(s).
 - K. After disease progression or the start of alternative anticancer therapy, all subjects (unless they have withdrawn consent) will be contacted approximately every 12 weeks by telephone, to assess survival until death or lost to follow up.

Table 12: Schedule of Assessments – Cohort 3

Day	Screening	Treatment Phase & Response Evaluation												SFU	Discontinuation follow-up ¹	Relapse/ Disease Progression	Long-term follow-up	
		Cycle 1		Cycle 2			Cycle 3			Cycles 4 -7	Cycles 10, 13, 16, 19, 22	Cycle 24	Cycle 24 q6 cycles					
		1	15	1	8	15	22	1	8	15	22	1	1	1	1			
Study Windows (days)	-28	±3		±3				±3				±3	±3	±3	±7	+7	±7	±7
Study Drug Administration ¹		CCI																
Acalabrutinib																		
Rituximab																		
Venetoclax																		
Procedures																		

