14.6.2 Secondary Endpoints

All secondary endpoints will be evaluated for each cohort separately. The ORR of the combination therapy of acalabrutinib plus venetoclax plus an anti-CD20 antibody at Cycle 16 (Cohorts 3 and 4) will be calculated and 95% exact binomial CIs will be provided. The CR rate and MRD-negative CR rate will be summarized. The degree of response will be summarized as well as the number of subjects who achieve CR but remain positive for MRD. Duration of response, time to CR, PFS, TTNT, time to response, and OS will be summarized with simple descriptive statistics obtained using the Kaplan-Meier method. DOR will be measured from the date of initial response to the date of disease progression or death. PFS will be measured from the date of first treatment to date of disease progression or death. For DOR and PFS, subjects who do not have disease progression or death will be censored at the date of last disease assessment. Subjects receiving stem cell transplant will be censored at the date of last disease assessment prior to the transplant. Time to next anti-CLL treatment will be measured from date of first treatment until date of next treatment or death, censoring those alive who have not started another treatment at last follow-up. OS will be measured from date of first treatment until date of death or last follow-up. These analyses will be useful in planning future studies.

Cytogenetic and molecular marker data, including FISH and stimulated karyotype results, Zap-70 methylation, and IGHV mutational status will be summarized for all subjects.

Relationships between these baseline variables and response rate or PFS will be explored graphically (e.g., side-by-side boxplots or Kaplan-Meier plots), where estimates with CIs will be presented as the primary method of analysis due to the limited number of subjects. If given a sufficient number of events, baseline markers may be correlated with response or survival using logistic regression or proportional hazards models, respectively, and adjusting for subject cohort (i.e., treatment-naïve versus relapsed/refractory).

Correlative studies will assess the effects of acalabrutinib alone or in combination with other study drugs on **CCI** as well as B, T, and NK cell numbers over the course of therapy. With these data collected serially over time, patterns will be explored graphically using box plots and/or individual time plots as well as analytically with repeated measures analysis of variance.

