7.0 Statistical Methods

7.1 Data Presentation

Tables and figures will be summarized by cohort unless otherwise specified.

No formal tests of hypotheses will be performed. P-values, if presented, will be provided for descriptive purpose. Descriptive statistics (number of subjects, mean, and standard deviation, median, minimum, and maximum) will be presented for continuous variables, including baseline demographic, disease characteristics, study drug administration, efficacy and safety outcomes. Categorical variables will be summarized as the number and percentage of subjects per category. Confidence intervals [CIs] may be included as appropriate.

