12.2.4 Duration of Response

Duration of response (DOR) is defined as the time from the date of achieving the first CR, CRi, nPR, or PR to the date of disease progression or death due to any cause, whichever comes first. Subjects who do not experience a disease progression or death will be censored using the same rule for PFS as described in Section 12.2.3.

DOR is calculated as date of disease progression or death (or censoring date for censored subjects) – date of achieving the first CR, CRi, nPR or PR + 1.

DOR will be analyzed similarly to PFS including a KM plot, as described in section 12.2.3.

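### SAP 12.2.3 censors PFS and DOR at the transplant date, whereas Protocol 14.6.2 uses the last disease assessment before transplant

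*SAP*

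**What the plan says.** **Protocol 14.6.2**, directly after its general censoring rule for DOR and PFS: "Subjects receiving stem cell transplant will be censored at the date of last disease assessment prior to the transplant".

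**SAP 12.2.3**: "If a subject receives an autologous or allogeneic stem cell transplant, the subject will be censored at the date of transplant". The transplant row of the censoring table gives the same date.

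**SAP 12.2.4** ties DOR to that rule: "Subjects who do not experience a disease progression or death will be censored using the same rule for PFS as described in Section 12.2.3".

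The rest of SAP 12.2.3 works differently. Its default is "If no disease progression or death is reported for a subject, the subject will be censored at the date of last adequate assessment". For a subject who starts other new therapy, "the subject will be censored at the date of last adequate assessment prior to receiving the new anticancer therapy". That new-therapy rule is an addition by the SAP; Protocol 14.6.2 has none for non-transplant therapy.

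On response criteria, Protocol Section 9 uses IWCLL 2008 for CLL and PLL, and the 2007 revised lymphoma criteria for SLL. SAP 12.0 names only the modified IWCLL criteria, with the 2012 lymphocytosis clarification, and mentions CLL and SLL together at the end of the sentence.

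**The concern.** The two current texts give different censoring dates for the same subjects, and the SAP neither flags nor explains the change. SAP 1.0 describes the SAP as giving the detail of analyses outlined in the protocol, so an unexplained change of rule is not covered by that purpose.

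The dates differ in substance. Between the last assessment and the transplant the subject is known to be alive but has not been checked for progression. Censoring at transplant credits that interval as progression-free and keeps the subject in the risk set through it. Any effect on PFS or DOR is in the favourable direction.

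The SLL wording is a separate and lesser matter. SLL is eligible only in Cohorts 1 and 2 (Protocol 3.1), and the SAP does not carry over the protocol's criteria for those subjects.

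**Working it through.** The plan states no figure that depends on this rule, so there is none to reproduce.

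**1. The rules side by side**

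| Situation | Protocol 14.6.2 | SAP 12.2.3 |
|---|---|---|
| No progression or death | last disease assessment | last adequate assessment |
| Transplant | last disease assessment before it | date of transplant |
| Other new therapy | no rule | last adequate assessment before it |
| No adequate assessment after first dose | no rule | date of first dose |

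Apart from transplant, the SAP table has six censoring rows. Five use the last adequate assessment. The sixth uses the first dose, and only when no such assessment exists. Transplant is the exception.

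**2. Length of the unassessed gap**

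SAP Appendix A places visits at day 28 × (cycle − 1) + 1; for example, C2D1 = 29 and C12D1 = 309. Ignoring windows and missed visits, the gap is at most one assessment interval. The SAP definition of an adequate assessment can be read to admit physical examination plus CBC without CT, so both cases are shown.

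- *Examination plus CBC, Cohorts 1 and 2.* Protocol Table 11 has Days 1, 8 and 15 of Cycle 1, then "Day 1 of Cycles 2-12". The gaps are 7, 7 and 14 days in Cycle 1, 28 days to Cycle 12, 84 days to Cycle 24 and 168 days after that.
- *Examination plus CBC, Cohorts 3 and 4.* 28 days to Cycle 7, up to 84 days to Cycle 24, then 168 days.
- *CT only.* Table 11 footnote B: "Response evaluations will be done every 12 weeks from randomization for the first 24 months", then every 24 weeks. The study is not randomised, so I count from first dose, as Appendix A does. The gap is up to 12 × 7 = 84 days, then 24 × 7 = 168 days. In Cohorts 3 and 4, after Cycle 36, it is 12 × 28 = 336 days.
- *Off treatment (Protocol 8.4).* Visits about every 84 days. CT every 168 days, then yearly after two years of that follow-up.

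The transplanted subject's own censored time lengthens by the part of the gap that has elapsed.

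**3. When the curve moves**

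The Kaplan-Meier estimate changes only at event times. A longer stay in the risk set matters only if another subject has an event inside the gap.

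SAP 12.2.3 dates progression at the assessment that documents it, and on-treatment subjects share one schedule counted from first dose. On-schedule progression therefore falls on a visit day. At the visit that opens the gap, the transplanted subject is at risk under both rules (a subject censored at a time counts as at risk at that time). At the visit that closes it, the subject has left under both. The risk sets are the same.

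What can fall inside the gap is:
- a death;
- progression at an unscheduled or off-window assessment;
- progression in a subject on the off-treatment clock;
- if only CT counts as adequate, progression found at an interim examination/CBC visit.

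This argument is for the PFS clock. DOR runs from first response, so visit days coincide less exactly. On the CT schedule of Cohorts 1 and 2, a Cycle 4 responder (day 85) has later visits at days 169 and 253, which are DOR days 85 and 169. A Cycle 7 responder (day 169) has visits at days 253 and 309, which are DOR days 85 and 141. An on-schedule progression at DOR day 141 can then lie inside the first subject's gap.

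**4. Size when it does move**

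With n at risk including one transplanted subject, and one other event in the gap, the SAP rule exceeds the protocol rule by S(t−) × [1/(n − 1) − 1/n]. At S(t−) = 1, the largest value for a given n:

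| n | SAP rule, 1 − 1/n | Protocol rule, 1 − 1/(n − 1) | Difference |
|---|---|---|---|
| 26 | 96.15% | 96.00% | 0.15 points |
| 19 | 94.74% | 94.44% | 0.29 points |
| 12 | 91.67% | 90.91% | 0.76 points |

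The values of n are the planned cohort sizes.

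**5. SLL criteria**

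SAP 12.0 can be read as applying IWCLL to SLL. Alternatively, its closing mention of CLL and SLL attaches only to the lymphocytosis clarification, and then no SLL criteria are stated. Neither reading reproduces Protocol Section 9.

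**The case against.** The case for leaving this alone is strong on consequence. No transplant is documented. PFS and DOR are secondary, no decision rule or sample size depends on them, and SAP 7.1 says "No formal tests of hypotheses will be performed". On-schedule progression leaves the PFS curve unchanged. All of that stands, and it sets the priority. It does not remove the contradiction or supply a reason for it.

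A reader might infer a material bias, since small late risk sets or several transplants would give larger shifts. The documents do not support that. It would need several transplants whose gaps all cover the same off-schedule event, and late in follow-up S(t−) is usually below 1, which shrinks the step. Nor is a long gap itself the error in the curve; alone, it lengthens only that subject's censored time.

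A reader might also infer that the primary response rate in Cohorts 1 and 2 is compromised by the SLL wording. One changed response would move it by 100/26 = 3.8 or 100/19 = 5.3 points. But investigators assess response, and the protocol gives them the SLL criteria. The number of SLL subjects is not stated, and nothing shows that any recorded response would change.

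Finally, Protocol 14.6.2 does not itself contain the term adequate assessment, a first-dose fallback or a qualifier about earlier progression. That is correct. The first two come from the SAP, and the third is a clarification that matches the SAP's new-therapy row.

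**Conclusion.** The conflict is real and the SAP is wrong as written: for transplanted subjects it departs from the protocol's PFS and DOR rule without a reason, and it is inconsistent with its own handling of other new therapy. The direction is fixed: upward or nil. The illustrated size is under one percentage point at any planned cohort size. It assumes one transplant, one other event inside the gap and no earlier drop in the curve. These figures are illustrations rather than bounds, and the actual effect may be zero because the number of transplants is not given. Priority is low. The SLL point is an alignment of wording only.

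**What to change.** In SAP 12.2.3, change both the text and the transplant row of the table. Subjects transplanted before documented progression or death should be censored at the last adequate assessment before the transplant, in line with Protocol 14.6.2. Keep the existing first-dose fallback for subjects with no such assessment. DOR then follows through SAP 12.2.4 without further edits.

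In SAP 12.0, state that CLL and PLL are assessed by IWCLL 2008 and SLL by the 2007 revised lymphoma criteria, with a reference to Protocol Section 9.

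The cost is a few lines of SAP text and a few lines of programming. No new data are needed.
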